ketoacidosis and growth attenuation have been reported in pediatric T1DM patients on a VLCD¹³, therefore, we anticipate low rates of these adverse events with the LCD intervention.

Aim 2 will provide preliminary estimates of the change in the atherogenic lipoprotein profile in patients on a LCD versus SCD. The primary outcome measure will be change in total LDL-P from baseline to 12 weeks after the nutrition intervention. As secondary outcomes, we will measure the change in other contributors to atherogenic lipoprotein load, such as high-density lipoprotein particle (HDL-P) number, small LDL-P number, and LDL size.

Aim 3 will provide preliminary estimates of the change in QOL in patients on a LCD versus SCD. Participants will complete the PedsQL, a validated QOL measure in T1DM patients, and Problem Areas in Diabetes-Teen (PAID-T), a validated measure of diabetes-specific distress, at baseline (week 0) and at 12 weeks after the nutrition intervention^{31,32}. Additionally, parents of participants will complete the WHO-5 Well-Being Index, a questionnaire for assessing subjective psychological well-being³³, and Problem Areas in Diabetes-Parent Revised version (PAID-PR), a validated measure of perceived parental burden associated with caring for a child with diabetes.³⁴

We will perform an independent samples t-test to compare outcomes between groups, in addition to multilinear regression analysis to account for potentially confounding covariates, such as total daily dose of insulin, weight change, glycemic variability as measured by continuous glucose monitoring (CGM), and age.

This proposed research will be the first prospective study to determine the effect of a LCD intervention on key diabetes outcomes in a pediatric T1DM population. This study will also provide a basis of training for a new pediatric investigator in the conduct of clinical trials under the mentorship of a highly successful mentorship team including [name] and [name].

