10.0 Statistical Considerations

10.1 Recruitment and Sample Size Justification

We have targeted an accrual of 40 participants in this pilot study to achieve two goals. First, we require a sufficient number of participants to estimate the effect size and variance of the LCD as a means to reduce HbA1c in T1DM in a future definitive trial. We utilized the method of Whitehead et al. to estimate our pilot study's optimum accrual, which proposes stepped increases in sample size based on the anticipated standard difference, d, between interventions 41,42 . We defined the minimum important difference (MID) in Δ HbA1c between LCD and SCD interventions as 0.3% and estimated a pooled SD of 0.8% based on our literature review9. If d=MID/SDpooled=0.3%/0.8%=0.38, a sample size of 20 participants per arm will optimize future sample size calculations for the definitive study, while allowing for up to 40% dropout. Second, this sample size allows for up to 4 degrees of freedom in multivariable linear regression analysis.

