10.2 Statistical Analysis

Statistical analysis will be performed using an independent samples t-test to compare change from baseline to 3 months post-intervention values from each aim (Δ HbA1c, Δ LDL-P, and Δ QOL score) between the two groups. We will also perform a series of multivariable linear regression analyses with change in primary outcomes from each aim (Δ HbA1c, Δ LDL-P, and Δ QOL score) from baseline to 12 weeks post-intervention as the dependent variable. Explanatory variables in the multivariable linear regression modeling will include mean total daily dose of insulin normalized for body mass, weight change, coefficient of variation of glucose as measured by CGM, and age.

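### The Section 10.2 regression names four covariates but no diet-group term, and adding that term takes the model past the 4 degrees of freedom stated in Section 10.1 unless that figure excludes it

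*Combined protocol and SAP*

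**What the plan says.** Section 10.1 sets the sample size: "We have targeted an accrual of 40 participants in this pilot study to achieve two goals". The first goal is to estimate effect size and variance for a later definitive trial, and the justification there ends "a sample size of 20 participants per arm will optimize future sample size calculations for the definitive study, while allowing for up to 40% dropout". The second goal concerns the regression: "Second, this sample size allows for up to 4 degrees of freedom in multivariable linear regression analysis". No rule is given for the figure of 4.

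Section 10.2 gives an independent-samples t-test of the change scores between two groups, and then a series of multivariable regressions of the same changes (HbA1c, LDL-P, QOL). For these it states: "Explanatory variables in the multivariable linear regression modeling will include mean total daily dose of insulin normalized for body mass, weight change". The sentence goes on to name the CGM glucose coefficient of variation and age. The group comparison is attached only to the t-test.

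Section 2.0 puts the two analyses in one sentence. It describes the t-test as comparing outcomes between groups and continues "in addition to multilinear regression analysis to account for potentially confounding covariates", naming the same four variables. Group is not listed as a term there either. Sections 2.0 and 6.1.1.6 describe three groups of 15.

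**The concern.** A regression whose only terms are insulin dose, weight change, glucose CV and age has no diet coefficient. It describes which covariates go with change in each outcome, pooled over diets, and can neither support nor qualify the t-test result. Yet Section 2.0 introduces it to deal with confounding, which has meaning here only in relation to the diet comparison. Group therefore appears to be intended, but it is not specified.

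Putting group in raises a second question. The four listed covariates already account for all of the df in Section 10.1, so the sections agree only if that figure leaves group out, which the text does not say.

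At stake is the adjusted analysis for all three aims. Whether group is in the model, how many levels it has and which covariates stay with it would all be left to decide after the data are seen, in a pilot meant to supply an effect estimate for a later trial.

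**Working it through.** **Inputs.** Section 10.1: 40 participants, 20 per arm, up to 40% dropout, up to 4 df. Section 10.2: four continuous covariates. Sections 2.0 and 6.1.1.6: three groups of 15.

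**1. The plan's own figure.** Section 10.1 gives no derivation. If one assumes 10 participants per df, 40/10 = 4, which matches. Assuming 15 gives 40/15 = 2.7, and 20 gives 40/20 = 2.0; neither matches. The 10-per-df rule is an inference, not something the plan states.

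**2. Model df.** Count one per continuous covariate, plus (groups − 1) for diet.
- As listed: 4, with no diet coefficient.
- Plus group, LCD versus SCD: 4 + 1 = 5.
- Plus group, three arms: 4 + 2 = 6.

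To stay at 4 df with group counted, at most 4 − 1 = 3 covariates fit with two levels, or 4 − 2 = 2 with three.

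**3. Can the larger model be fitted?** Yes. At n = 40 the residual df are 40 − 5 − 1 = 34. Participants per df fall from 40/4 = 10 to 40/5 = 8.

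**4. Precision cost of the one extra df (two-group model).** Compare group plus four covariates with group plus three. Assume normal covariates that do not predict the outcome and are unrelated to group. Relative to no covariates, the variance of the group coefficient with p covariates is then (n − 3)/(n − 3 − p). The residual df are n − 2 − p. Going from p = 3 to p = 4, the ratio of 95% CI half-widths is

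√[(n − 6)/(n − 7)] × t(n − 6)/t(n − 5).

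The number analysed is uncertain, so a range is shown: 40; 30 (two groups of 15); 24 (40 × 0.6); 18 (30 × 0.6).

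| n | √[(n − 6)/(n − 7)] | t(n − 6)/t(n − 5) | Half-width ratio |
|---|---|---|---|
| 40 | √(34/33) = 1.015 | 2.032/2.030 | 1.016 |
| 30 | √(24/23) = 1.022 | 2.064/2.060 | 1.024 |
| 24 | √(18/17) = 1.029 | 2.101/2.093 | 1.033 |
| 18 | √(12/11) = 1.044 | 2.179/2.160 | 1.053 |

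The extra df costs about 2% to 5%.

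**5. A comparison not to confuse with this.** Four non-predictive covariates against none give ratios of 1.06, 1.09, 1.13 and 1.20 at the same n. Three against none already give 1.046, 1.066, 1.090 and 1.139. Most of that widening is the price of adjusting at all, and would remain after trimming to three covariates.

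**The case against.** The best reply is that group is plainly implied. Section 2.0 ties the regression to the between-group comparison, and the wording in Section 10.2 says what the variables will include, which need not be a closed list. This largely stands. A reader might infer that the sponsor means to fit a model pooled over diets, or that the trial would have no diet estimate. The documents do not support either inference: the likelier explanation is an unnamed term, and the t-test gives the unadjusted effect for every aim.

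The second reply is that the 4 df may mean four adjustment covariates on top of group. That is possible, since exactly four are listed. A reader might infer a definite breach of a stated limit. Section 10.1 does not go that far, because it neither derives the figure nor says what it counts. However, it speaks of the regression as a whole, so the ambiguity still needs resolving.

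Third, the 40% dropout allowance belongs to the first goal in Section 10.1. The df statement should not be read as a promise about completers, and the smaller n above only show a range.

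Fourth, a reader might attribute 6% to 20% wider intervals to the extra df. That range compares four covariates with none. The non-predictive case is also unfavourable, since predictive covariates could narrow the interval.

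**Conclusion.** The point holds as a specification gap in a supporting analysis. As listed, the Section 10.2 regression gives no adjusted diet effect, although Section 2.0 says it is there to adjust the group comparison. With group added it has 5 df (two groups) or 6 df (three arms), against a stated 4 whose scope is undefined.

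The df count and the absence of a group term follow directly from the text. The precision cost, about 2% to 5% for one extra df over n = 40 down to 18, rests on non-predictive covariates and the two-group model. The model can be fitted and the primary comparison is unaffected. The case for correcting the plan rests on fixing the adjusted estimate in advance, not on lost precision. It should be corrected before analysis.

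**What to change.** In Section 10.2:
- Name diet group as an explanatory variable and state whether it has two or three levels.
- Report its coefficient (LCD minus SCD, 95% CI) for each aim as the adjusted estimate, alongside the t-test and not in place of it.
- State the time point of each covariate.

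Then reconcile with Section 10.1 in one of two ways.

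1. **Trim to 4 df, group included.** Keep at most three covariates with two levels, or two with three levels. The choice should not be made by count alone. Drop first those measured after randomisation: weight change, and glucose CV or insulin dose if on-study values are meant. Section 2.0 makes CGM glycemic variability a secondary outcome of Aim 1, so on-study glucose CV may itself respond to diet, and adjusting for such variables could remove part of the diet effect. Keep baseline variables such as age.
2. **Restate the 10.1 figure.** Say whether it counts group, and give it for the model actually fitted and the number expected to be analysed.

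The change is to wording only. The cost is one or more dropped covariates, or a slightly less favourable df statement.

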2.0 Rationale and Specific Aims

We hypothesize that pediatric patients with T1DM who consume a LCD will have improved HbA1c compared with T1DM patients who consume a standard-carbohydrate diet (SCD). We further hypothesize that differences in lipidemia and quality of life (QOL) between the groups will be minimal. To test our hypotheses, we will employ a pragmatic nutrition education intervention. The study will randomize adolescent patients (ages 13-21 years) to one of three groups (n = 15per group). We will instruct participants to consume a LCD (group 1) or a SCD (group 2), or provide no specific recommendations regarding diet (group 3). We will prescribe isocaloric diets for groups 1 and 2 equaling the estimated energy requirements of the Institute of Medicine⁷. Participants on the SCD intervention will consume 45-65% of total daily caloric intake from carbohydrates, 25-35% from fat and 10-30% from protein. Participants on the LCD intervention will consume 25-35% of total daily intake from carbohydrates, 45-65% from fat and 10-30% from protein. Group 3 will serve as a control that receives the same number of education sessions as groups 1 and 2 to teach general diabetes management but without specific dietary recommendations. This study design will allow for discrimination of the effect of the composition of the diet versus the effect of receiving any nutritional prescription.

Nutrition interventions are effective in producing dietary behavior change among adolescents²⁷, particularly when information and communication technologies (ICT) are incorporated²⁸. Previous brief nutrition interventions teaching LCD or low glycemic index diets in T1DM patients have resulted in appropriate dietary adherence^{29,30}. We will provide both traditional and ICT-based education and monitor dietary adherence with a smart-phone based nutritional tracking tool.

Aim 1 will provide preliminary estimates of improvement HbA1c after a nutrition intervention that teaches a LCD versus education reinforcing a SCD to families of pediatric T1DM patients. To determine the primary outcome—change in HbA1c—we will obtain HbA1c at baseline and at 12 weeks after the nutrition intervention. Additionally, we will quantify glycemic variability using continuous glucose monitoring (CGM) as a secondary outcome. Low rates of severe hypoglycemia, diabetic

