6.1.1.5 Insulin Pump Instructions

The study team will instruct T1DM participants in the use of an insulin pump such as Medtronic Minimed 670G, Tandem T-Slim, or Omnipod Insulim Management System for the administration of insulin during the study. Instructions will include administering all insulin via insulin pump and recording all carbohydrates consumed into the insulin pump. The

team will then show T1DM participants how to upload insulin pump data into a HIPAA and FDA-compliant cloud-based, data-integration platform such as Medtronic Careline or Tidepool. The team will show the control participants how to use the insulin pump device during this time.

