6.1.2 Run In Period (Weeks -2 to 0)

Participants will log all dietary intake in the smartphone nutritional tracking app, which will serve as a baseline of dietary habits. They will also be instructed to consistently wear the CGM and to administer insulin boluses using their pump's bolus calculator.

Participants in groups 1 and 2 will be asked to complete nutritional tracking in the smartphone app during this time. Participants in group 3 will be asked to complete a blood sugar and exercise log.

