Carbohydrate quantity and type affect post-prandial glycemia more than any other dietary factor in non-diabetic populations^{4,5}. Additionally, consuming larger meals is associated with underestimation of carbohydrate quantity and mealtime insulin dose, leading to increased glucose variability⁵. These findings serve as the theoretical basis for implementing a carbohydrate restricted diet to improve HbA1c and decrease glycemic variability with the ultimate goal to prevent CVD.

7.3 Assessment of risk to adolescent participants relative to 45 CFR part 46, subpart D

It is our impression that T1DM subjects would fall under 45 CFR 46.406, as outlined in Vanderbilt's Human Research Protections Program Policy Number IX.A, section II.C. The proposed research is likely to yield generalizable knowledge about these adolescents' condition. Specifically,

- 7.3.1 The risk represents a minor increase over minimal risk.
- 7.3.2 The procedure presents experiences to participants that are reasonably commensurate with those inherent in their actual or expected medical situation.
- 7.3.3 The procedure is likely to yield generalizable knowledge about the participants' disorder or condition, which is of vital importance for the understanding or amelioration of the participants' disorder or condition.

7.3.4 Adequate provisions are made for soliciting assent of the children and permission of their parents or legal guardians as detailed in the present IRB application.

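### The additional regression in section 10.2 adjusts for weight change and for insulin dose and glucose CV of unstated timing, and does not list arm; with on-diet values an arm coefficient would not be the total LCD-SCD effect

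*Combined protocol and SAP*

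**What the plan says.** Section 10.2 puts an independent-samples t-test first, on change to 12 weeks in HbA1c, LDL-P and QOL. It then adds multivariable regressions of the same changes, with explanatory variables "mean total daily dose of insulin normalized for body mass, weight change, coefficient of variation of glucose as measured by CGM, and age". No measurement window is given for insulin dose or CV, and randomised arm is not in the list.

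Section 2.0 presents the regression alongside the between-group comparison, as a way to "account for potentially confounding covariates, such as total daily dose of insulin, weight change" and similar variables. The same section says under Aim 1 that "we will quantify glycemic variability using continuous glucose monitoring (CGM) as a secondary outcome". Section 7.2.1 gives as the theoretical basis "implementing a carbohydrate restricted diet to improve HbA1c and decrease glycemic variability", and section 1.0 says the same.

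The pump and CGM data are downloaded at week 0 (6.1.3.3) and at week 12 (6.1.6.3). Randomisation is described at the week −2 visit (6.1.1.6) and the diets start at week 0 (6.1.3.6). Section 10.1 says the pilot is to supply an effect size and variance for a definitive trial, and allows up to 4 model degrees of freedom.

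**The concern.** A confounder of a randomised comparison would have to influence the outcome and differ between arms for reasons other than the diet. A variable that the diet itself changes is a consequence of treatment, and conditioning on it removes or distorts part of the effect being estimated.

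- **Weight change** is a consequence by construction, though its LCD-SCD difference may be small because both diets are designed to maintain weight (6.1.3.6).
- **Glucose CV**, measured on diet, is a quantity that the protocol expects carbohydrate restriction to lower.
- **Insulin dose**, measured on diet, is tied to carbohydrate by the plan's own procedures. Instructions include "administering all insulin via insulin pump and recording all carbohydrates consumed into the insulin pump", and in the run-in participants are told to "administer insulin boluses using their pump's bolus calculator". "Participants on the LCD intervention will consume 25-35% of total daily intake from carbohydrates", against 45–65% on SCD.

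At stake is the meaning of the adjusted estimate. With on-diet covariates it answers a different question from the t-test, while the confounding label invites a reader to take it as the corrected answer. Section 10.1 does not say which of the two estimates will inform the definitive trial.

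**Working it through.** **The plan's own figure.** Section 10.1 has MID 0.3% and pooled SD 0.8%. 0.3/0.8 = 0.375, which rounds to the stated 0.38. The SD is taken below as the SD of change in HbA1c.

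**Degrees of freedom.** The four listed covariates use 4 df, exactly the limit in 10.1. As literally written, the model therefore has no diet contrast. Adding arm makes 5 df for two arms and 6 for three.

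**Shift from one on-diet covariate (HbA1c).** Let r be the within-arm correlation of covariate and outcome change, and delta the number of SDs by which LCD lowers the covariate. The within-arm slope is 0.8r per SD, so with a true effect of −0.30:

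expected adjusted coefficient = −0.30 + 0.8 × r × delta

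The documents give neither r nor delta, so these are assumed values:

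| delta | r = −0.5 | r = −0.3 | r = −0.1 | r = 0.1 | r = 0.3 | r = 0.5 |
|---|---|---|---|---|---|---|
| 0 | −0.30 | −0.30 | −0.30 | −0.30 | −0.30 | −0.30 |
| 0.3 | −0.42 | −0.37 | −0.32 | −0.28 | −0.23 | −0.18 |
| 0.6 | −0.54 | −0.44 | −0.35 | −0.25 | −0.16 | −0.06 |

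OLS simulation (6,000 replicates; 15, 12 and 9 per arm; ignorable losses) agreed. At r = 0.3, delta = 0.6 the formula gives −0.156 and the simulated means were −0.150 to −0.159. Unadjusted means stayed at −0.29 to −0.30. In a separate simulation with 20 per arm, pre-diet CV in place of on-diet CV left the arm coefficient at −0.299 to −0.306.

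Two covariates can add or cancel. With delta 0.6 each and a correlation of 0.3 between them, the coefficient is −0.08 if both r are 0.3, and −0.30 if they are 0.3 and −0.3.

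**How large delta could be for insulin dose (assumption only).** At the range midpoints, prescribed carbohydrate is 1 − 30/55 = 45% lower on LCD. Assume that boluses are 40–60% of total dose, that between-person CV is 25–40%, and that boluses scale with carbohydrate at unchanged pump settings. Then delta runs from 0.455 × 0.4/0.40 = 0.45 to 0.455 × 0.6/0.25 = 1.09 with full adherence, and is half that with half adherence. It is 0 with no adherence or if dose changes offset it.

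**Against the uncertainty.** The t-test 95% half-width, t(2n−2) × 0.8 × √(2/n), is 0.512 for 20 per arm (10.1) and 0.598 for 15 per arm (6.1.1.6). After 40% dropout it is 0.677 (12 per arm) and 0.799 (9 per arm). For delta up to 0.6 and |r| up to 0.5, the largest single-covariate shift is 0.24, under half of any of these. At delta 1.09 and r = 0.5 it would be 0.8 × 0.5 × 1.09 = 0.44, which is 73% of 0.598 and 85% of 0.512.

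**What a pre-diet model would buy.** Adjusting for the week-0 outcome multiplies the SE by √((1+rho)/2), where rho is the week-0/week-12 correlation (equal SDs assumed). For rho 0.5 to 0.8 that is 0.866 to 0.949. The half-widths below use arm plus three covariates (2n−5 residual df), with the expected cost of chance imbalance in all three, √(1 + 3/(2n−6)):

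| n per arm | t-test | rho 0.5 | rho 0.8 |
|---|---|---|---|
| 20 | 0.512 | 0.464 | 0.508 |
| 15 | 0.598 | 0.553 | 0.605 |
| 12 | 0.677 | 0.639 | 0.700 |
| 9 | 0.799 | 0.789 | 0.864 |

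At rho 0.8 the interval is 1%, 3% and 8% wider than the t-test's at 15, 12 and 9 per arm.

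**The case against.** The strongest reply is that little rests on this model. The t-test comes first, the regression is an addition, the aims promise preliminary estimates, and no decision rule uses the adjusted coefficient. Section 10.1 defines its MID and SD on unadjusted change, which points to the unadjusted estimate for planning. All of this stands and limits the severity. It does not settle which estimate serves the definitive trial, because 10.1 does not say.

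A second reply is that week-0 insulin dose and CV may be what is meant. That may be so, which is why the point is conditional for those two. It does not help weight change. Week-0 values are pre-diet but are collected after randomisation. LCD and SCD share the same run-in tasks, so a shift between them is unlikely, but group 3 differs: "Participants in group 3 will be asked to complete a blood sugar and exercise log".

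A third is that the sizes are assumed. That is correct. The insulin delta rests on figures from outside the documents, and fixed pump settings are doubtful: endocrinologists manage doses throughout (6.1.3) and closed-loop users are included (5.3). No size can be given for LDL-P or QOL, for which no SD is stated.

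A reader might infer that the main diet comparison is biased, or that the regression will understate the LCD effect. The documents support neither. The t-test contains none of these covariates. The sign of r is unknown, so the coefficient could move either way or not at all.

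**Conclusion.** The point holds for the additional regression only. Weight change is post-randomisation, the timing of insulin dose and CV is unstated, and the plan treats glycemic variability both as an outcome of the diet and as a possible confounder of it. If on-diet values enter, an arm coefficient from this model is not the total LCD-SCD effect. For HbA1c the shift is 0.8 × r × delta per single covariate, with size and sign unknown and zero if the diet does not move the covariate. That an arm coefficient is intended is inferred from section 2.0; taken literally, section 10.2 yields no diet contrast at all.

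The t-test on change is untouched by these points. Its own freedom from bias still requires that the week-0 exclusions (6.1.3), on-study removals (6.1.4) and dropout are ignorable. Severity is minor to moderate: confidence in the principle is high, and no particular size is claimed.

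**What to change.** In section 10.2:

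- Name randomised arm in the model.
- For the adjusted diet effect, use only pre-diet covariates: the week-0 value of the outcome and, as df allow, the stratification factors age and pump-loop status. With arm this is 4 df for two arms and 5 for three.
- Take weight change and on-diet insulin dose and CV out of that model. Report them as outcomes, or in a model labelled exploratory; the four-covariate model can be kept there.
- If insulin dose or CV stays as a covariate, state that the week-0 value is used, count its df, and note the different run-in tasks of group 3.
- Keep the t-test on change.

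In section 10.1, say which estimate serves the definitive trial. Restate the df for the sample size actually planned (40 in total there; 15 in each of three groups in 6.1.1.6) and after the allowed dropout. In section 2.0, replace the confounding label.

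The cost is text edits, since the variables are already planned for collection. The 4-df model leaves 19 residual df from 24 completers or 13 from 18, against 18 or 12 for the listed covariates plus arm. The case for the change is a clear estimand. The precision gain is modest at best and can become a small loss in the smaller samples shown above, so a leaner model with arm and the week-0 outcome is reasonable if dropout is heavy.

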6.1.6.2 Blood draw

Blood will be drawn from each participant and the following labs obtained:

- HbA1c
- Beta hydroxybutyrate
- NMR spectroscopy lipoprofile.

6.1.6.3 Continuous glucose monitor and insulin pump data collection

Continuous glucose monitor and insulin pump will be downloaded into a HIPAA and FDA-compliant cloud-based, data-integration platform such as Dexcom Clarity, Medtronic Carelink, or Tidepool.

Information that will be collected from the continuous glucose monitor download will include (but not be limited to):

- Percent of time spent above the glycemic target of 140 mg/dL
- Percent of time spent in the glycemic target of 70 140 mg/dL
- Percent of time spent below the glycemic target of 70 mg/dL
- Percent of time spent in hypoglycemia below 50 mg/dL
- Average blood glucose
- Blood glucose standard variation

Information that will be collected from the insulin pump download will include (but not be limited to):

- Average total daily dose of insulin
- Average bolus amount of insulin per day
- Average basal amount of insulin per day

6.1.6.4 Nutritional tracking smartphone application data collection

Participants in groups 1 and 2 will be asked to complete nutritional tracking in the smartphone app during this time.

Participants in group 3 will be asked to complete a blood sugar and exercise log.

Information that will be collected from the smartphone app will include (but not be limited to):

- Total number of calories consumed
- Average grams of carbohydrates consumed per day
- Average grams of fat consumed per day
- Average grams of protein consumed per day
- Additional macronutrient data

Participants will also be asked to photograph all food consumed in the 24 hours prior to the study visit. At the study visit, they will complete a 24 hour dietary recall.

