7.1.2 Hypoglycemia

Hypoglycemia is encountered intermittently by patients with T1DM as part of the natural consequence of diabetes management with exogenous insulin administration, and we do not anticipate that this risk will be increased by consuming a low carbohydrate diet.

One study surveyed an online social media group of pediatric T1DM patients who consumed a very low-carbohydrate diet (VLCD) with an average carbohydrate intake goal of 36 grams per day and found low rages of adverse events, including hypoglycemia with seizure or coma (2%), hypoglycemia requiring assistance from others (12%), and hypoglycemia requiring glucagon (4%)¹³. We anticipate that the rates of these events will be considerably lower in the current study given that the carbohydrate intake in both the low-carbohydrate and standard-carbohydrate groups will be substantially higher than in the previously mentioned study.

We will use the following safety provisions to minimize risk of hypoglycemia: Participants will wear a continuous glucose monitor throughout the study period and will be instructed to contact the study team for any episode of hypoglycemia (blood glucose <70). If hypoglycemia occurred, the study team would instruct the patient to be treated orally (administer 15 grams of carbohydrates in liquid form or with glucose tablets) if the patient is responsive and able to consume the treatment orally. If the patient is unresponsive, the study team would instruct the participant's caretaker to administer intramuscular glucagon. The study team will ensure that the participants have an up to date glucagon kit at time of enrollment.

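### Section 10.2 uses CGM glucose variability, a declared Aim 1 secondary outcome, only as a covariate, and no section compares time in low glucose between the diets

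*Combined protocol and SAP*

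**What the plan says.** Section 2.0, under Aim 1, states that "we will quantify glycemic variability using continuous glucose monitoring (CGM) as a secondary outcome". Later in the same section the general analysis statement reads "We will perform an independent samples t-test to compare outcomes between groups". That sentence goes on to list CGM variability among the possible confounders for the regression. Section 2.0 therefore gives the same measure two roles.

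Section 10.2 keeps only one of them. Its t-test covers the change in three measures, "Δ HbA1c, Δ LDL-P, and Δ QOL score) between the two groups". Its regressions take those same three changes as dependent variables. The explanatory variables are insulin dose per body mass, weight change, "coefficient of variation of glucose as measured by CGM, and age". The section does not say whether the CV comes from the run-in or from the diet period.

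Sections 6.1.3.3 and 6.1.6.3 list the CGM downloads at weeks 0 and 12. Both include "Percent of time spent below the glycemic target of 70 mg/dL", time below 50 mg/dL, average glucose and its spread. No section names a low-glucose measure as an outcome or compares one by diet.

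Sections 1.0 and 7.2.1 give the rationale: restricting carbohydrate should improve HbA1c and reduce glycaemic variability.

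**The concern.** There are two linked gaps.

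First, the plan expects the diet to change glucose variability. If variability during the diet period is held fixed in the HbA1c regression, the diet coefficient no longer describes the whole effect of assigning the diet. It describes what remains after any part that runs through, or moves with, variability has been taken out. Meanwhile the effect on variability, promised as a secondary outcome, has no estimate in the analysis section.

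Second, HbA1c follows mean glucose. It falls when high readings are removed and also when low readings are added. The data that help to separate these are collected at both visits, but no planned analysis uses them by arm. The Aim 1 estimate is meant to inform a later definitive trial, so its reader will want to know whether low glucose contributed.

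**Working it through.** **1. The plan's own figures.** The plan gives no figure for this point. The nearest are in section 10.1: a minimum important difference of 0.3% and an SD of 0.8% for change in HbA1c. Their ratio is 0.3/0.8 = 0.375, which the plan rounds to 0.38.

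**2. Each CGM measure, section by section.**

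| Measure | Collected (6.1.3.3, 6.1.6.3) | Role in 2.0 | Role in 10.2 |
|---|---|---|---|
| Variability (CV) | Mean and spread, weeks 0 and 12 | Secondary outcome and covariate | Covariate only |
| Time below 70 mg/dL | Weeks 0 and 12 | None | None |
| Time below 50 mg/dL | Weeks 0 and 12 | None | None |

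**3. What adjustment for on-study CV does.** Let δ be the effect of LCD versus SCD on CV, and β the slope of change in HbA1c on CV at fixed diet. In a linear model, total diet effect = adjusted diet coefficient + β × δ. The adjusted coefficient equals the total effect only if β or δ is zero, and the rationale in 1.0 and 7.2.1 expects δ to be below zero. The documents give neither β nor δ, so the loss cannot be sized. This step assumes that diet group is in the regression, although 10.2 does not list it, and that CV is taken on study.

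**4. How much HbA1c could low glucose account for? (Illustration only.)** Assumed, not in the documents: 5 or 10 more points of the day at 60 mg/dL instead of 140 or 180, and 25 to 35 mg/dL of mean glucose per 1% HbA1c. Fall in mean glucose = share of day × (starting level − 60).

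| Shift | From | Fall in mean (mg/dL) | HbA1c fall at 35 | HbA1c fall at 25 |
|---|---|---|---|---|
| 5 points | 140 | 0.05 × 80 = 4 | 0.11% | 0.16% |
| 5 points | 180 | 0.05 × 120 = 6 | 0.17% | 0.24% |
| 10 points | 140 | 0.10 × 80 = 8 | 0.23% | 0.32% |
| 10 points | 180 | 0.10 × 120 = 12 | 0.34% | 0.48% |

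A 5-point shift never reaches 0.3%. A full 0.3% needs a fall of 0.3 × 25 = 7.5 to 0.3 × 35 = 10.5 mg/dL. That is 7.5/120 = 6.3% to 10.5/80 = 13.1% of the day, or about 1.5 to 3.2 hours.

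**5. Could severe events stand in for CGM data? (Illustration only.)** With an assumed 12-week risk of 1% or 3% per participant, the chance of no event among 15 is 0.99^15 = 0.86 or 0.97^15 = 0.63.

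**6. Precision of the added estimates.** Half-width of the 95% interval for a difference between two arms, in SD units: t(0.975, 2n − 2) × √(2/n). Section 10.1 gives 20 per arm, and 2.0 and 6.1.1.6 give 15. The last two rows apply the 40% dropout allowed in 10.1.

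| n per arm | t | √(2/n) | Half-width (SD) |
|---|---|---|---|
| 20 | 2.024 | 0.316 | 0.64 |
| 15 | 2.048 | 0.365 | 0.75 |
| 12 | 2.074 | 0.408 | 0.85 |
| 9 | 2.120 | 0.471 | 1.00 |

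The documents give no SD for time below range. If the SD of its change were 2, 3 or 5 points, the half-width at 15 per arm would be 1.5, 2.2 or 3.7 points. For HbA1c itself it is 0.748 × 0.8 = 0.60%.

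**The case against.** *Variability is compared after all.* The t-test sentence in section 2.0 speaks of outcomes in general, and variability is a declared outcome. A reader who concludes that the plan nowhere compares variability goes too far. What stands is narrower: 10.2 omits it, and both sections also use it as a covariate. The sentence does not help time below 70 or 50 mg/dL, which is never named as an outcome.

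*Low glucose is watched closely.* CGM data are reviewed continuously (6.1.4.1) and at telephone visits (6.1.5), and participants report any reading below 70 (7.1.2). A shift large enough to produce a whole 0.3% fall would be hard to miss. That is true, but it is monitoring of individuals. Sections 8.4 to 8.6 deal with unanticipated events, whereas hypoglycaemia is an anticipated risk, and no table by arm is planned. Section 6.1.4 also removes participants after severe hypoglycaemia and states no rule for their outcome data.

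*A fall caused by low glucose would be reported as better control.* A reader might infer this. The documents do not support it: they set no rule for such a conclusion, Aim 1 promises preliminary estimates, and nothing prevents the CGM summaries from being shown.

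*Section 7.1.2 contradicts itself.* It says "we do not anticipate that this risk will be increased by consuming a low carbohydrate diet" and then "We anticipate that the rates of these events will be considerably lower in the current study given that the carbohydrate intake in both" study diets is higher than in the survey. A reader might see a conflict. The first statement concerns this trial's LCD against the usual risk in T1DM. The second compares both trial diets with a survey diet of 36 g a day. Risk could rise at very low intake and not at 25–35% of energy, so the two are compatible.

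*The added intervals will be wide.* This stands. It argues for estimation rather than testing, which is what a pilot is for.

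**Conclusion.** The point holds in limited form. Section 10.2 leaves a declared secondary outcome without an analysis and uses it as a covariate. If CV is taken on study, the adjusted HbA1c coefficient can miss part of the diet effect. Time below 70 and below 50 mg/dL is collected but not compared by diet, so an HbA1c difference could be interpreted with no planned look at the contribution of low glucose.

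Neither effect can be sized from the documents. The HbA1c range and the severe-event probabilities rest on assumed inputs and are illustrations. They suggest that low glucose is plausible as a partial contributor, that it would have to be extensive to explain a whole 0.3% difference, and that counts of severe events among 15 participants are a poor substitute for CGM data. The change is worth making because it removes a possible bias and uses data already in hand.

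**What to change.** In section 10.2:

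- Remove on-study glucose CV from the covariates of the main HbA1c model. If adjustment is wanted, use the week 0 value and say so. Section 6.1.1.6 places randomisation before the run-in, so this value precedes diet instruction rather than allocation. LCD and SCD participants have the same run-in tasks (6.1.2).
- Add LCD minus SCD estimates with 95% confidence intervals for change from week 0 to week 12 in glucose CV, percent time below 70 mg/dL and percent time below 50 mg/dL. Present them beside the HbA1c result and label them as estimates, not tests.
- Bring section 2.0 into line, so that CGM variability is an outcome and is not also listed as an on-study confounder.

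The cost is SAP wording and a few extra analysis lines on data already downloaded. No new measurement is needed. The price in interpretation is wide intervals: about 0.75 SD either side at 15 per arm, and about 1.00 SD at 9 completers per arm.
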